8. PATIENT FOLLOW-UP

All patients will recover from their procedures according to standard practice. They will remain NPO the night after the procedure. After finishing the procedure, all patients will be carefully monitored per standard protocol in the recovery room and be discharged when fully awake and pain-free. Patients will be contacted by telephone at 24-48 hours to ascertain and document any early adverse events that may have arisen. Long-term clinical follow up will be based on clinical indications.

To determine the safety of procedure, all pre, intra- and immediate post-procedure adverse events will be recorded and rated according to ASGE lexicon (7) for adverse events. Inpatients will be evaluated by study coordinator/PI on a daily basis during their hospitalization. Potential complications will be explained for patients at their discharge time and will be advised to refer whenever they have problems.

- a. Study duration and number of study visits required of research participants. Study duration: 2 years Number of subjects: 132 Follow-up visits: 0
- Blinding, including justification for blinding or not blinding the trial, if applicable.
 Due to the nature of study, treatment team will be aware of patient's group and it is not possible to make it double blinded. However, the study pathologist will be blinded to randomization.

- Justification of why participants will not receive routine care or will have current therapy stopped.
 Routine care will be followed
- d. Justification for inclusion of a placebo or non-treatment group. N/A
- e. Definition of treatment failure or participant removal criteria. The first randomization assigned EUS sampling technique will be used until adequate specimen is achieved (up to 3 passes total). After 3 passes, the patient will undergo the other EUS sampling technique until adequate specimen is achieved (up to 3 passes total). If inadequate biopsies are obtained after a total of 6 passes (3 with initial tissue acquisition techniques, 3 with the other technique), the endosongrapher will be permitted to utilize any EUS sampling technique preferred to obtain a diagnosis during the same procedure or at a later date.
- f. Description of what happens to participants receiving therapy when study ends or if a participant's participation in the study ends prematurely. No change in medical care will be expected.

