12. STATISTICAL CONSIDERATIONS

Overview: This study is designed as a non-inferiority trial.

Considering a success rate of 85% in the FNA with ROSE group, based published studies, we selected a non-inferiority margin (∂) of 10%, in accordance with the USFDA recommendations (8). Based on the following formula (9):

n = f(α, β) × [πs × (100 – πs) + πe × (100 – πe)] / (πs – πe – d)2

where πs and πe are the true percent 'success' in the standard and experimental treatment group respectively, and

 $f(\alpha, \beta) = [\Phi - 1(\alpha) + \Phi - 1(\beta)]2$

 Φ -1 is the cumulative distribution function of a standardized normal deviate

We calculated that our trial will require enrolling 120 patients for power of 80% and two sided α of 0.05.

Taking into consideration a 10% dropout rate, the total patients to be enrolled=132

Baseline demographics, pre-, intra- and post-intervention data will be prospectively collected on data collection forms which will be maintained in an electronic database system. Results will be reported as mean ± standard deviation (SD) for quantitative variables and percentages for categorical variables. The groups will be compared using the Student's t- test or Wilcoxon rank sum test for continuous variables and the chi-square test (or Fisher's exact test if required) for categorical variables. To compare

diagnostic accuracy between two EUS sampling techniques, we will use McNemar's test. Statistical significance will be based on two-sided design-based tests evaluated at α = 0.05. All statistical analyses will be performed using STATA.

a. Endpoints:

Primary:

Diagnostic accuracy will be defined as (true positive + true negative)/all samples. The final diagnosis will be based on one of the following criteria: (i) surgical pathology specimen from patients who underwent surgical resection; (ii) cytological or histopathological diagnosis of malignancy in patients with unresectable disease with appropriate imaging and clinical course of disease; (iii) cytological and histopathological diagnosis of benign disease with an appropriate clinical course of disease for minimum of 6 months.

Secondary:

1. Specimen adequacy

This will be defined as the proportion of samples in which a final histopathological diagnosis could be made.

2. Percentage of histology cores obtained

This will be defined as the proportion of samples in which a visible histology core biopsy was obtained

- 3. Number of passes Number of passes required for diagnosis

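### Enrolling 132 patients covers about 9% dropout, not the stated 10%: a 10% loss leaves an expected 118.8, just under the 120 required

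*Combined protocol and SAP*

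**What the plan says.** The sample-size paragraph of section 12 (Statistical Considerations) ends in two steps. The requirement comes first: "We calculated that our trial will require enrolling 120 patients", for 80% power and "two sided α of 0.05". The allowance for losses follows: "Taking into consideration a 10% dropout rate, the total patients to be enrolled=132". Section 8 (Patient Follow-up), item a, repeats the total: "Number of subjects: 132".

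The plan does not say which number the 10% is a percentage of, and gives no source for it. No other section defines the dropout rate differently or sets another target.

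**The concern.** A dropout rate is normally a share of the patients who enter the trial. To have 120 left after losing 10% of entrants, 120 must be divided by 0.90. The plan appears to have multiplied 120 by 1.10, which always gives too small a number. The total of 132 would then fall short of the plan's own requirement under its own dropout assumption.

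What is at stake is whether the sample-size statement is consistent. The enrolment total stands in two sections, and anyone checking the paragraph will find that its three figures do not agree. The gap itself is very small.

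**Working it through.** **Inputs.** Required number 120, dropout rate 10% and total 132 (all section 12); total 132 again (section 8, item a).

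**1. Reproduce the plan's figure.** 120 × (1 + 0.10) = 132. The match is exact, so 12 patients, 10% of the required number, were added.

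**2. Apply the stated rate to those enrolled.** 132 × (1 − 0.10) = 118.8. The shortfall is 120 − 118.8 = 1.2 expected patients, or 1.2/120 = 1.0%. In general, N(1 + d)(1 − d) = N(1 − d²). With d = 0.10 the shortfall is 1% of whatever required number N is used, so the step would be wrong for any other N as well.

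**3. Find the dropout that 132 covers.** (132 − 120)/132 = 12/132 = 9.1%.

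**4. Find the total that fits both 120 and 10%.** 120/(1 − 0.10) = 133.3. Enrolling 133 leaves 133 × 0.90 = 119.7, which is still short. Enrolling 134 leaves 134 × 0.90 = 120.6. The matching total is 134, two more than planned.

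**5. See whether the 120 can be turned into a statement about power.** Section 12 gives 85% success for FNA with ROSE, a margin of 10 points, 80% power and two-sided α of 0.05. Its formula also needs πe, the success rate for FNB, and no value is given. Trying values in the plan's formula:

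- πe = 85%, one-sided 0.025 (the equivalent of two-sided 0.05): f = (1.960 + 0.842)² = 7.849, and n = 7.849 × (85 × 15 + 85 × 15)/(85 − 85 − 10)² = 7.849 × 2550/100 = 200.1, so 201 per group.
- πe = 85%, one-sided 0.05: 6.183 × 2550/100 = 157.7, so 158 per group.
- A total of 120 (60 per group) needs πe of about 91.4% at one-sided 0.025, or about 90.0% at one-sided 0.05.
- If 120 is the formula's n for each technique, πe must be about 87.5% at one-sided 0.025, or about 86.3% at one-sided 0.05.

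Several unstated assumptions therefore lead to 120, and the plan does not say which was used. The formula is also for two independent groups. Section 7 (Procedure Plan) has every patient undergo both techniques, and section 12 compares accuracy by McNemar's test. Power in that design depends on how often the two techniques disagree, which the plan does not state. Steps 1 to 4 do not depend on any of this.

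**The case against.** The strongest reply is that the plan never names the denominator of its 10%. Read as an allowance of 10% on top of the required number, 132 is exact. On that view the plan uses a loose convention and does not contradict itself. The 10% is also a round figure without a source, and the difference between 9.1% and 10% is well within the uncertainty of such a guess. The plan speaks of enrolling 120 and does not call them evaluable. Finally, since 120 is itself in doubt, correcting the next step may be pointless, or may suggest that 120 is sound.

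The part about size stands: this is a small correction, and no decision about running the trial turns on it. The part about wording does not rescue the figure. The plan calls the 10% a dropout rate, and patients drop out of those enrolled. The word used beside 120 does not help either. The next sentence adds patients for dropout and calls 132 the total to be enrolled, so 120 can only be the number wanted after losses. Doubt about 120 does not make the inflation step right, since multiplying by 1.10 under-covers a 10% loss whatever the starting number.

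**Conclusion.** The point holds as a minor arithmetic error. The figures 120, 10% and 132 cannot all stand: 132 covers 9.1% dropout, and a 10% loss leaves an expected 118.8, which is 1.2 below 120. This rests on two assumptions: 120 is taken as given, and the dropout rate is read as a share of those enrolled.

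A reader might infer more, namely that the trial will miss its 80% power. If 120 gave exactly 80% at two-sided 0.05, scaling by Φ(√(n/120) × (1.960 + 0.842) − 1.960) would give 79.3% at 118, 79.6% at 118.8 and 79.7% at 119. The documents do not support that premise. No πe is stated, the formula assumes independent groups, and the planned comparison is paired with no discordance rate given. The true power at 120 is unknown from the plan, so a loss of 0.3 to 0.7 points cannot be attributed to it.

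Nor does the point show that more patients must be enrolled. The inconsistency can be removed by restating the allowance.

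**What to change.** Change one sentence in section 12, in one of these ways:

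- Keep 132 and state that it allows for about 9% dropout (12 of 132). This is the simplest.
- Keep 132 and 10%, and state that about 118.8 patients (118 to 119) are expected to remain. Do not attach a power figure to that number, because the plan's stated inputs do not allow one to be calculated.
- If the sponsor wants to keep both 120 and 10%, state 134.

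The first two options add no patients and leave section 8, item a, as it is. Their only cost is a slightly less favourable statement of the allowance or of the number expected to remain. The third adds two patients and requires section 8, item a, to read 134.

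If 120 is re-derived for the paired design, divide the new requirement by (1 − dropout rate), round up, and update the total in both section 12 and section 8, item a.

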1. OBJECTIVES

The objective of this single center paired cohort study is to evaluate the diagnostic accuracy of EUS-FNA with ROSE compared to EUS-FNB without ROSE. If EUS-FNB without ROSE is shown to be non-inferior to the current standard of care of EUS-FNA with ROSE in pancreatic lesions, this study has the potential to make EUS-guided tissue acquisition more economical (with elimination for the need for cytopathology staff onsite) as well as provide core histological specimen without sacrificing the overall diagnostic yield.

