7. PROCEDURE PLAN

All EUS/FNB and EUS/FNA will be performed using a linear array echoendoscope by one of seven experienced EUS physicians at JHH. All patients will undergo both EUS/FNB and EUS/FNA. Patients will be randomized to either FNB or FNA first by

means of computer-generated numbers. The endoscopist will not be blinded to the randomization; however, the study pathologist will be blinded to randomization.

EUS/FNB will be performed using similar techniques for tissue acquisition as FNA using 22-g FNB needle (Medtronic SharkCore or Boston Scientific Acquire). Lesions will be identified using EUS and punctured with the 22-g FNB needle (10-15 back and forth movements per needle pass, fanning as appropriate). After the lesion is punctured, the stylet will be removed and 10cc suction will be applied. FNB samples will be placed directly into formalin containers and sent to be processed by surgical pathology.

EUS/FNA with ROSE will be performed using standard techniques via 22-g FNA needle (Cook Medical EchoTip Ultra or Boston Scientific Expect or Medtronic Beacon). Lesions will be identified using EUS and punctured with the FNA needle (10-15 back and forth movements per needle pass, fanning as appropriate). After the lesion is punctured, the stylet will be removed and 10cc suction will be applied. FNA specimens will be processed for ROSE using standard techniques with bedside smear slide evaluation and liquid-based cytology and cell-block preparation.

The first randomization assigned EUS sampling technique will be used until adequate specimen is achieved (up to 3 passes total). After 3 passes, the patient will undergo the other EUS sampling technique until adequate specimen is achieved (up to 3 passes total). If inadequate biopsies are obtained after a total of 6 passes (3 with initial tissue acquisition techniques, 3 with the other technique), the endosonographer will be permitted to utilize any EUS sampling technique preferred to obtain a diagnosis during the same procedure or at a later date.

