13. SAFETY MONITORINGN AND STOPPING RULE

The DSMB will perform a blinded analysis after enrolment and initial outpatient followup of 50% of the study cohort.

Interim analysis will be performed at 50% recruitment. If a > 20% difference in sensitivity is found between both methods then the study will be terminated early

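### The 10-point non-inferiority margin enters no analysis or decision rule; the only named primary test is a two-sided McNemar test of equal accuracy

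*Combined protocol and SAP*

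**What the plan says.** Section 1 makes the trial's conclusion conditional: "If EUS-FNB without ROSE is shown to be non-inferior to the current standard of care of EUS-FNA with ROSE". Section 12 opens with "This study is designed as a non-inferiority trial" and continues "we selected a non-inferiority margin (∂) of 10" percent, against an assumed 85% success rate for FNA with ROSE. The margin then appears as d in the sample-size formula and nowhere else.

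The analysis paragraph of Section 12 names one method for the primary endpoint: to compare "diagnostic accuracy between two EUS sampling techniques, we will use McNemar's test". The next sentence sets the criterion for all tests: "Statistical significance will be based on two-sided design-based tests evaluated at α = 0.05".

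The data are paired. Section 7 states "All patients will undergo both EUS/FNB and EUS/FNA", and only the order is randomized.

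The only other numeric decision threshold is the interim rule in Section 13, under which the study stops if a more than 20% "difference in sensitivity is found between both methods then the study will be terminated early". That rule concerns a different measure and a different threshold. No section gives a confidence interval for the paired difference, a test with a null hypothesis shifted to the margin, or a rule for declaring non-inferiority.

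**The concern.** A non-inferiority claim requires rejecting the hypothesis that FNB is worse by 10 points or more. McNemar's test addresses a different hypothesis, that the two techniques are equally accurate. Its possible outcomes map onto the objective as follows:

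- **Significant, favouring FNB.** This implies non-inferiority.
- **Not significant.** This is compatible with non-inferiority and also with a deficit beyond the margin. The test does not tell them apart.
- **Significant, favouring FNA.** This shows a deficit but does not say whether it lies within 10 points.

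The middle outcome is the expected one if the techniques perform alike, and the plan does not say what will be concluded from it. At stake is a possible change of practice, namely dropping on-site cytopathology, on the strength of a test that cannot support it. There is a second risk. With no interval method or rule fixed in advance, both could be chosen after the data are seen.

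**Working it through.** **Inputs from Section 12:** margin 10 points; FNA success 85%; two-sided alpha 0.05; power 80%; 120 evaluable patients. **Not in the documents:** the assumed FNB success rate, and the discordance rate psi (the proportion of patients in whom exactly one technique is correct). I assume psi of 15%, 20%, 25.5% and 32.5%. The last two are the values under independence: 2 × 0.85 × 0.15 = 0.255 for 85% each, and 0.85 × 0.25 + 0.15 × 0.75 = 0.325 for 85% versus 75%.

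**The plan's own figure.** With 85% in both groups and one-sided 0.025, the Section 12 formula gives (1.960 + 0.842)² × (85 × 15 + 85 × 15) / 10² = 7.849 × 25.5, about 200.1, so 201 per group. The stated 120 is not reproduced under that assumption. This is a separate sample-size matter, and the present point does not depend on it. I use n = 120 below because it is the stated evaluable number.

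**Formulas.** Let b be the number of patients with only FNA correct, c the number with only FNB correct, and n = 120.

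- McNemar: chi-square = (b - c)² / (b + c), compared with 3.84.
- Difference (FNB minus FNA): D = (c - b) / n.
- Wald standard error: √[b + c - (b - c)²/n] / n.
- Paired score test (Tango) at d0 = -0.10: z = (D - d0) / √[(2q + d0 - d0²)/n], where q is the maximum-likelihood estimate of P(only FNA correct) when the difference is fixed at d0. Non-inferiority is shown if z > 1.96.

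**Example 1: b = 12, c = 6.** Chi-square = 36/18 = 2.0, p = 0.16 (exact p = 0.24). D = -6/120 = -5.0 points. Standard error = √(18 - 36/120)/120 = √17.7/120 = 0.0351. Wald lower limit = -5.0 - 1.96 × 3.51 = -11.9; score lower limit = -12.5. There is no significant difference, yet non-inferiority is not shown.

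**Example 2: b = c = 19.** Chi-square = 0, p = 1.00, D = 0. Standard error = √38/120 = 0.0514. Lower limit = -10.1 (Wald) or -10.2 (score). Non-inferiority fails even at identical observed accuracy. This is a borderline table: 18 versus 18 just passes, with a score limit of -9.99.

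**Operating characteristics.** Exact enumeration over all (b, c) at n = 120, with the uncorrected chi-square McNemar test.

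True deficit of 10 points, where any non-inferiority claim is an error:

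| psi | McNemar non-significant | Score test claims NI | Wald interval claims NI |
|---|---|---|---|
| 15% | 14.7% | 2.1% | 3.4% |
| 20% | 27.7% | 2.3% | 3.3% |
| 25.5% | 39.8% | 2.4% | 3.0% |
| 32.5% | 51.2% | 2.5% | 2.7% |

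Equal true accuracy:

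| psi | McNemar non-significant | Score test shows NI | Non-significant, NI not shown by score test |
|---|---|---|---|
| 15% | 94.9% | 76.1% | 21.4% |
| 20% | 94.7% | 65.5% | 31.9% |
| 25.5% | 94.8% | 56.9% | 40.6% |

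At equal accuracy, a significant result favouring FNB, the one outcome from which the named test supports the claim, occurs in about 2.5% of trials.

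**The case against.** The strongest reply is that the harm is conditional. Nowhere does the plan say that a non-significant McNemar result will be read as non-inferiority, so the 15% to 51% figures describe a possible misreading and not the error rate of a stated rule. That is correct, and the figures should be quoted only with that condition. It does not rescue the plan: without the misreading, there is no route to the stated conclusion unless FNB is significantly better.

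The size also depends on discordance, which with a true 10-point deficit could be as low as 10%. At 11% and 12%, McNemar's test is non-significant in only 2.8% and 5.9% of trials (5.3% and 9.4% with the exact version). This stands as a qualification. Those cases need FNB alone to be correct in just 0.5% or 1% of patients, since (11 - 10)/2 = 0.5 and (12 - 10)/2 = 1. At the other end, 32.5% assumes that two techniques applied to the same lesion give independent results, which is probably an upper case.

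One may also say that McNemar's test is right for paired data, and that a stated margin implies the usual interval rule. The first is true; the fault lies in the null hypothesis and not in the pairing. The second asks the reader to supply a rule that the plan does not contain, in place of the test that it names. The choice of interval is not neutral either: at a true 10-point deficit and 15% discordance, the Wald interval errs in 3.4% of trials and the score test in 2.1%.

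**Conclusion.** The concern holds, and it must be fixed before the primary analysis. The plan states a non-inferiority objective and a margin, then names an analysis that does not use the margin. This follows from the text alone and would be true at any sample size.

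The numerical size rests on 120 pairs, an assumed discordance rate and the uncorrected McNemar test. If non-significance were taken as non-inferiority, the false-claim rate at the margin would be about 6 to 20 times the nominal 2.5% for discordance between 15% and 32.5% (14.7/2.5 = 5.9; 51.2/2.5 = 20.5), and much closer to nominal at 11% to 12%. Ordinary outcomes are affected as well: at equal true accuracy and discordance of 15% to 25.5%, 21% to 41% of trials would give a non-significant McNemar result while failing to show non-inferiority by the score test.

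**What to change.** Replace the primary analysis statement in Section 12 with three elements:

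1. The estimate is the within-patient difference in diagnostic accuracy, FNB without ROSE minus FNA with ROSE, with a two-sided 95% confidence interval from one paired method named in advance. The Tango score interval is suitable; another valid paired interval, or a test shifted to the margin, would also serve.
2. Non-inferiority is declared only if the lower limit is above -10 percentage points.
3. McNemar's test is kept for superiority and done only after non-inferiority is shown.

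This changes wording only and needs no new data. It does expose the separate question of sample size. With no true difference, 120 pairs give score-interval power of 88%, 76%, 65% and 57% at assumed discordance of 10%, 15%, 20% and 25.5%. The Wald interval gives 81% at 15%. Whether the stated 80% is reached therefore depends on the discordance rate and the method, and both should be stated when the rule is written.

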1.1 STUDY DESIGN

Multicenter, Prospective, Single Blind, Randomized clinical trial. Patients will be randomly allocated (Using computerized software) with a 1:1 ratio either to the EUS-FNA with ROSE or FNB first group.

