- 4. Rate of technical failures

Technical failure was defined as the inability to perform the procedure, including the need to change the needle

5. Adverse events

All pre, intra- and immediate post-procedure adverse events will be recorded and rated according to ASGE lexicon for adverse events.

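### The primary endpoint divides by samples rather than patients, so a technique that yields no specimen drops out of the accuracy comparison instead of counting against it

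*Combined protocol and SAP*

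**What the plan says.** The primary endpoint in section 12 reads: "Diagnostic accuracy will be defined as (true positive + true negative)/all samples". The word samples is not defined there or elsewhere.

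Other parts of the plan point to the patient as the unit. Section 7 states: "All patients will undergo both EUS/FNB and EUS/FNA". Section 1.1 randomises only the order, "with a 1:1 ratio either to the EUS-FNA with ROSE or FNB first group". To compare "diagnostic accuracy between two EUS sampling techniques, we will use McNemar's test", says section 12, and that test needs one result per technique per patient. Section 7 also limits each technique to three passes.

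Technical failure is a separate secondary endpoint in section 12: "Technical failure was defined as the inability to perform the procedure, including the need to change the needle". No sentence says how a technique with no specimen is scored in the primary analysis.

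Rescue sampling is described in section 7. "If inadequate biopsies are obtained after a total of 6 passes", three with each technique, then "the endosonographer will be permitted to utilize any EUS sampling technique preferred to obtain a diagnosis during the same procedure or at a later date". Section 8, item e, repeats this under a heading about treatment failure and removal of participants, without saying which of the two applies.

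**The concern.** A denominator made of samples counts only what was obtained. If a needle cannot be used in a patient, or brings back nothing, there is no sample to put in the ratio. McNemar's table also has no entry for that patient unless a rule supplies one. The failure would then be reported under a secondary endpoint and would have no effect on the primary result.

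This matters more here than in a superiority trial. The claim sought is that FNB without ROSE is not worse than FNA with ROSE by 10 points. Removing failures of the experimental technique moves the observed difference towards zero, which is the direction that supports the claim. In practice the relevant quantity is how often a technique gives the right answer in patients in whom it is attempted, and a failed attempt belongs in that figure.

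**Working it through.** **Inputs from section 12.** FNA success is 85%, the margin is 10 points, and 120 patients are required before dropout. No technical failure, no-specimen or inadequacy rate is given anywhere, so every failure rate below is an assumption shown over a range.

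**The plan's own figure.** The 120 does not follow from the stated inputs. With both success rates at 85%, the section 12 formula gives 201 per group at one-sided 0.025 and 158 at one-sided 0.05. That is a separate matter. The argument here does not depend on the sample size, and 120 is used only for scale: one patient is 1/120 = 0.83 points, and the margin is 0.10 x 120 = 12 patients.

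**Effect on one technique.** Suppose accuracy is 85% where a specimen exists and a share f of patients gives none. Counting those patients as not accurate gives 0.85 x (1 - f):

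- f = 1%: 84.2%
- f = 2%: 83.3%
- f = 5%: 80.8%
- f = 10%: 76.5%

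Dividing by samples reports 85% in every case.

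**Effect on the comparison.** Let the true per-patient accuracy, with failures counted, be 75% for FNB and 85% for FNA, so that FNB lies exactly at the margin. Drop FNB-only failures in a share f of patients, and assume FNA is 85% accurate in the patients who remain.

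| f | FNB as reported, 0.75/(1 - f) | Apparent difference from 85% |
|---|---|---|
| 2% | 76.5% | -8.5 points |
| 5% | 78.9% | -6.1 points |
| 10% | 83.3% | -1.7 points |

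**Allowing for the lost pair.** Dropping the pair also removes that patient's FNA result. If a is FNA's accuracy in the dropped patients, the apparent difference is (-0.10 + f x a)/(1 - f). At f = 5%:

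- a = 0.85: (-0.10 + 0.0425)/0.95 = -6.1 points, as in the table
- a = 1: (-0.10 + 0.05)/0.95 = -5.3 points
- a = 0: -0.10/0.95 = -10.5 points

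The difference therefore shrinks when FNA mostly succeeded where FNB failed. It does not shrink when both failed in the same patients.

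**Direction.** If the 5% were FNA-only failures, with FNB at 75% in the patients who remain, FNA would be reported as 0.85/0.95 = 89.5% and the apparent difference would be 75 - 89.5 = -14.5 points. This works against FNB.

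**The case against.** The strongest reply is that the intended unit is clear enough. Every patient has both techniques and McNemar's test is named, so one result per technique per patient is implied. That is a fair reading of the unit, but it does not say what result to enter when a technique gives no specimen.

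Second, a non-diagnostic sample is still a sample. It is neither a true positive nor a true negative, so the formula already counts it as not accurate. This stands, and on that point the fix only puts the rule into words.

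Third, a technical failure does not always mean no specimen, because the definition includes a needle change after which sampling may succeed. Lesions that EUS cannot reach are excluded, and both techniques use 22-gauge needles in a similar way, so one-sided failures may be rare. This also stands. It limits the likely size of the effect but does not close the gap.

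A reader might go further and infer that rescue samples are credited to whichever technique the endosonographer chooses, so that reported accuracy is not that of the capped technique. The documents do not support this. They neither include nor exclude rescue samples. The stated purpose of rescue is to reach a diagnosis, and the section 8 heading suggests failure or removal, neither of which credits a technique. Rescue also follows only when both techniques were inadequate, and it shifts the difference only if credited unequally.

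The largest figure for that reading overstates it. Taking 15% failure per technique, both fail in 0.15 x 0.15 x 120 = 2.7 patients if independent, or 0.15 x 120 = 18 if fully concordant. Half rescued by one technique gives 1.35/120 = 1.1 to 9/120 = 7.5 points. But the 15% is inaccuracy, which includes wrong diagnoses on adequate specimens, and these do not trigger rescue. At an assumed 5% inadequacy the same steps give 0.3 to 6 patients, or 0.1 to 2.5 points.

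**Conclusion.** The concern holds for missing specimens. As written, the denominator lets a technique's failure to produce a specimen leave the primary analysis, although the design and test are per patient. With FNB-only failures of 2%, 5% or 10%, a true deficit of 10 points would appear as about 8.5, 6.1 or 1.7 points.

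These sizes rest on assumed failure rates, on failures confined to FNB, and on FNA being 85% accurate in the remaining patients. Failures mainly on FNA would push the other way, and failures shared by both techniques would not favour FNB. The plan therefore does not guarantee a false claim of non-inferiority. It leaves the result open to a bias of unknown size and direction that a scoring rule would remove.

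The status of rescue samples is a secondary clarification. The plan is silent on it, and silence does not show that they count.

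**What to change.** In section 12, define accuracy for each technique as true positives plus true negatives, divided by all randomised patients who start the procedure. Then state that:

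- each patient contributes one result per technique, taken only from that technique's protocol-capped passes;
- a technique with no specimen, or a non-diagnostic specimen, is scored as not accurate;
- a needle change followed by a specimen within the capped passes is scored on that specimen and still counted under the technical-failure endpoint;
- rescue samples, in the same session or later, may contribute to the final diagnosis but never to either technique's accuracy, adequacy or pass count;
- a sensitivity analysis is restricted to patients with a specimen from both techniques.

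The cost is a few sentences and a case report form flag separating protocol passes from rescue passes. Reported accuracy may fall slightly. The fix changes scoring only, leaves the sampling procedure as it is, and should be settled before outcome data are seen.
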